13.2.4 Access to Records

The investigator will make the office and/or hospital records of subjects enrolled in this study available for inspection by Vertex or its representative at the time of each monitoring visit and for audits. The records will also be available for direct inspection, verification, and copying, as required by applicable laws and regulations, by officials of the regulatory health authorities (FDA and others). The investigator will comply with applicable privacy and security laws for use and disclosure of information related to the research set forth in this protocol.

13.2.5 Subject Privacy

To maintain subject confidentiality and to comply with applicable data protection and privacy laws and regulations, all CRFs, study reports, and communications relating to the study will identify subjects by assigned subject numbers and access to subject names linked to such numbers shall be limited to the site and the study doctor and shall not be disclosed to Vertex. As required by applicable laws and regulations in the countries in which the study is being conducted, the investigator will allow Vertex and/or its representatives access to all pertinent medical records to allow for the verification of data gathered in the CRFs/SAE forms and the review of the data collection process. The FDA and regulatory authorities in other jurisdictions, including the IRB/EC, may also request access to all study records, including source documentation, for inspection.

For sites participating in the study in the US, and in accordance with the Health Insurance Portability and Accountability Act and associated regulations (“HIPAA”) an executed HIPAA authorization shall be obtained by the site from each subject (or the legal representative of the subject) before research activities may begin. Each HIPAA authorization shall comply with all HIPAA requirements including authorization allowing the site access to and use of the subject’s personally identifiable health information, authorization for the site to disclose such information to Vertex, the FDA and other parties requiring access under the Protocol, and statements as to the purpose for which such information may be used and for how long.

13.2.6 Record Retention

The investigator will maintain all study records according to ICH GCP guidelines and/or applicable local regulatory requirement(s), whichever is longest, as described in the Clinical Study Agreement. If the investigator withdraws from the responsibility of keeping the study records, custody will be transferred to a person willing to accept the responsibility and Vertex will be notified.

13.2.7 Study Termination

At any time, Vertex may terminate this study in its entirety or may terminate this study at any particular site. In addition, for reasonable cause, either the investigators or their IRBs/IECs may terminate the study at their center.

Conditions that may lead to reasonable cause and warrant termination include, but are not limited to:

- Subject or investigator noncompliance
- Unsatisfactory subject enrollment
- Lack of adherence to protocol procedures
- Lack of evaluable and/or complete data
- Potentially unacceptable risk to study subjects
- Decision to modify drug development plan
- Decision by the FDA or other regulatory authority

Written notification that includes the reason for the clinical study termination is required.

13.3 Data Quality Assurance

Vertex or its designated representative will conduct a study site visit to verify the qualifications of each investigator, inspect clinical study site facilities, and inform the investigator of responsibilities and procedures for ensuring adequate and correct study documentation.

The investigator is required to prepare and maintain adequate and accurate case histories designed to record all observations and other data pertinent to the study for each study participant. Study data for each enrolled subject will be entered into a CRF by study site personnel using a secure, validated web-based electronic data capture (EDC) application. Vertex will have read-only access to site-entered clinical data in the EDC application.

Instances of missing, discrepant, or uninterpretable data will be queried with the investigator for resolution. Any changes to study data will be made to the CRF and documented in an audit trail, which will be maintained within the clinical database.

13.4 Monitoring

Monitoring and auditing procedures developed or approved by Vertex will be followed to comply with GCP guidelines. On-site checking of the CRFs/SAE Forms for completeness and clarity, cross-checking with source documents, and clarification of administrative matters will be performed.

The study will be monitored by Vertex or its designee. Monitoring will be done by personal visits from a representative of Vertex or designee (study site monitor), who will review the CRFs/SAE Forms and source documents. The study site monitor will ensure that the investigation is conducted according to the protocol design and regulatory requirements.

13.5 Electronic Data Capture

Vertex will provide the study sites with secure access to and training on the EDC application sufficient to permit study site personnel to enter or correct information in the CRFs on the subjects for which they are responsible.

A CRF will be completed for each enrolled study subject. It is the investigator's responsibility to ensure the accuracy, completeness, clarity, and timeliness of the data reported in the subject's CRF. Source documentation supporting the CRF data will indicate the subject's participation in the study and will document the dates and details of study procedures, AEs, other observations, and subject status.

The investigator, or designated representative, will complete the CRF as soon as possible after information is collected.

The audit trail entry will show the user's identification information and the date and time of any correction. The investigator will provide formal approval of all the information in the CRFs, including any changes made to the CRFs, to endorse the final submitted data for the subjects for whom the investigator is responsible.

Vertex will retain the CRF data and corresponding audit trails. A copy of the final archival CRF in the form of a compact disc or other electronic media will be placed in the investigator's study file.

13.6 Publications and Clinical Study Report

13.6.2 Clinical Study Report

A clinical study report, written in accordance with the ICH E3 Guideline, will be submitted in accordance with local regulations.

4 INTRODUCTION

This statistical analysis plan (SAP) is for the final analysis and interim analysis (IA) of study VX15-210-101 and is based on the

- approved clinical study protocol, 14 April 2017, Version 2.0
- approved eCRF, dated May 24 2018, Version 4.0

VX15-210-101 is a Phase 2b/3, double-blind, randomized, placebo-controlled multicenter study. This study will assess the efficacy and safety of VX-210 in subjects with acute traumatic cervical spinal cord injury.

This SAP (Methods) documents the interim and final efficacy and safety analysis and data presentation for VX15-210-101.

SAS® Version 9.4 Software (SAS Institute, Cary, North Carolina, USA) or higher will be used to generate all statistical outputs (tables, figures, listings and datasets).

The SAP (Methods) Version 1.0 was finalized and approved before the data cut for the interim analysis. The interim analysis methods specified in Section 10.1 of the SAP (Methods) Version 1.0 were implemented during the interim analysis. Any revisions to the approved SAP (Methods) Version 1.0 will be documented and approved prior to the final clinical database lock and treatment unblinding for the study.

Any changes made to the SAP (Methods) after the clinical data lock has occurred will be documented in the clinical study report for this study.

The analysis addressing the pharmacokinetic (PK) objective of the study will be described in the Clinical Pharmacology Analysis Plan (CPAP) which will be developed separately by the Clinical Pharmacology department at Vertex Pharmaceuticals Incorporated (Vertex). The independent data monitoring committee (IDMC) analyses are also described in a separate SAP.

5 STUDY OBJECTIVES

5.1 Primary Objective

Evaluation of the efficacy and safety of VX-210 treatment is the primary objective of the study.

5.2 Secondary Objectives

- Neurological recovery: examination of the effects of VX-210 on the recovery of sensation and motor activity
- Daily function: analysis of the impact of VX-210 on activities of daily living (ADLs) and requirements for attendant care

6 STUDY ENDPOINTS

6.1 Primary Endpoint

Change from baseline in upper extremity motor score (UEMS) at 6 months after treatment

6.2 Secondary Endpoints

- Spinal Cord Independence Measure (SCIM) III Self-Care subscore at 6 months after treatment
- Capabilities of Upper Extremity Test (CUE-T) score at 6 months after treatment
- Graded Redefined Assessment of Strength, Sensibility and Prehension (GRASSP) Quantitative Prehension score at 6 months after treatment
- American Spinal Injury Association Impairment Scale (AIS) grade conversion from baseline to 6 months after treatment
- Motor level change from baseline to 6 months after treatment
- Pharmacokinetic (PK) parameters of VX-210

7 STUDY DESIGN

7.1 Overall Design

[figure not shown]
This is a multicenter, randomized, double-blind, placebo-controlled study to examine the efficacy and safety of VX-210 treatment. The study will be conducted at approximately 45 sites in the United States and Canada and will enroll approximately 100 male or female subjects 14 to 75 years of age (inclusive) with acute traumatic SCI, C4 to C7 (motor level) on each side, and AIS grade A or AIS grade B. Subjects will be randomized to receive a single 9-mg dose of VX-210 in fibrin sealant or a placebo (buffer solution) in fibrin sealant at a 1:1 ratio until approximately 100 subjects are enrolled (approximately 50 subjects in each treatment arm: 9-mg VX-210 and placebo). Subjects will be stratified by age (<30 versus ≥30 years of age) and AIS grade (A versus B with sacral pinprick preservation versus B without sacral pinprick preservation) when they are randomized to the 2 study arms. The 1-time dose of VX-210 or placebo will be administered by a surgeon directly to the dura mater of the spinal cord at the site of injury during decompression/stabilization surgery that commences within 72 hours after the initial injury.

For an individual subject, the study will last approximately 12 months. Follow-up appointments after the initial hospital stay will be at 6 weeks, 3 months, 6 months, and

12 months after treatment. At specified time points during the study, subjects will be evaluated for medical, neurological, and functional changes, and serum will be collected for PK and immunological analyses.

A schematic of the study design is provided in [Figure 7-1](#).

Figure 7-1 Schematic of Study Design

7.2 Sample Size and Power

The primary efficacy endpoint is the change from baseline in UEMS at 6 months after treatment.

The null hypothesis to be tested is that the mean change from baseline in UEMS at 6 months after treatment is the same for 9-mg dose of VX-210 and placebo. This null hypothesis will be tested at 2-sided significance level $\alpha = 0.05$.

The sample size was calculated using a projected standard deviation (SD) of 6.0, based on the variability of improvement in UEMS scores of cervical subjects in the historical Sygen database. Anticipated withdrawal of 10% of subjects before the first follow-up assessment was also included in the sample size calculation.

If 9-mg dose group improves in UEMS by 4 points over placebo (a clinically meaningful increase), a total of approximately 100 subjects (approximately 50 per arm) will have approximately 82.1% power to detect a statistically significant treatment effect for 9-mg dose group compared to placebo, considering the interim futility analysis.

Based on the review of data from Anderson et al., the SD was projected to be 3.8 for SCIM III Self-Care subscore. [Table 7-1](#) presents the estimated power for detecting various

treatment differences between an active treatment group and the placebo group in SCIM III Self-Care subscore, assuming 45 randomized subjects with follow-up assessment in each treatment group without considering the possible power loss from the interim futility analysis.

Table 7-1 Power Estimates Under a Variety of Treatment Differences, Given 45 Randomized Subjects With Follow-up Assessments in Each Treatment Group

Mean Difference in SCIM III Self-Care Subscore	Power (%)
1	23
2	69
3	95

Power estimates are based on 2-sided t-test with $\alpha = 0.05$.

7.3 Randomization

Subjects will be randomized to receive a single 9-mg dose of VX-210 in fibrin sealant, or a placebo (buffer solution) in fibrin sealant at a 1:1 ratio. Subjects will be stratified by age (<30 versus ≥ 30 years of age) and AIS grade (A versus B with sacral pinprick preservation versus B without sacral pinprick preservation) when they are randomized to the 2 study arms.

An interactive web or voice response system (IXRS) will be used to assign subjects to treatment. The randomization code will be produced by Vertex Biostatistics or a qualified randomization vendor. The Vertex study biostatistician will review and approve the dummy randomization list. The final randomization list will be generated and approved by an unblinded biostatistician or designee who is not a member of the study execution team.

7.4 Blinding and Unblinding

This will be a randomized double-blind study.

7.4.1 Blinding

All Vertex study personnel will be blinded to subject treatment assignments, except for the following individuals: an external vendor biostatistician preparing the final (production) randomization list who is not part of the Study Execution Team (SET); Bioanalytical CRO analyzing PK samples and the Vertex Bioanalytical staff who needs to review the raw data from Bioanalytical CRO (excluding Bioanalytical SET member who will continue to be blinded); and Vertex Global Patient Safety (GPS) and Regulatory Affairs representatives when required to satisfy regulatory reporting requirements.

7.4.2 Unblinding

At the initiation of the study, the study site will be instructed on the method for breaking the blind. The unblinding method will be either a manual or electronic process.

Unblinding of the individual subject's treatment by the investigator will be limited to medical emergencies or urgent clinical situations in which knowledge of the subject's study treatment

is necessary for clinical management. In such cases, investigators will use their best judgment as to whether to unblind without first attempting to contact the medical monitor to discuss and agree to the need for unblinding. If investigators deem it not necessary to unblind immediately, they will first attempt to contact the medical monitor to discuss and agree to the need for unblinding. If investigators have tried, but are unable to reach the medical monitor, they will use their best judgment, based on the nature and urgency of the clinical situation, and may proceed with unblinding without having successfully reached and discussed the situation with the medical monitor.

Contact information for the medical monitor (or appropriate backup) will be provided in a separate document.

In addition, the Vertex Medical Information Call Center [REDACTED] will answer calls 24 hours a day, 7 days a week, 365 days of the year, and will triage these calls to the study medical monitor or appropriate backup.

If a subject's treatment assignment has been unblinded for a medical emergency or urgent clinical situation, the medical monitor will be notified within 24 hours of the unblinding event. The reason and the date of the unblinding will be documented clearly in the subject's study file. Information about the treatment assignment obtained from the unblinding will be maintained in a secure location with controlled access and will not be shared with the sponsor (Vertex), contract research organization (CRO), or any site personnel (other than the physician treating the subject). In addition, the investigator will consider whether the clinical event that prompted unblinding will be considered an SAE, according to the regulatory definitions or criteria for SAEs, and if so, submit an SAE report to Vertex GPS or designee, per Section 13.1.2 of the protocol.

Vertex GPS or designee will also unblind any SAE reports in compliance with regulatory reporting requirements. In addition, Vertex may, for matters relating to safety concerns, unblind individual subjects at any time.

8 ANALYSIS SETS

8.1 All Subjects Set

The All Subjects Set is defined as all subjects who have been randomized or have received study drug. This analysis set will be used in subject listings and disposition summary table, unless otherwise specified.

8.2 Full Analysis Set

The Full Analysis Set (FAS) is defined as all randomized subjects who have received study drug. The FAS is to be used in efficacy analyses in which subjects will be analyzed according to their randomized treatment group and not to the treatment they actually received.

8.3 Safety Set

The Safety Set is defined as all subjects who have received study drug. The Safety Set is to be used for all safety analyses in which subjects will be analyzed according to the treatment they received and not according to their randomized treatment group.

9 STATISTICAL ANALYSIS

9.1 General Considerations

The Schedule of Assessments is provided in [Appendix A](#).

The precision standards for reporting safety and efficacy variables are provided in an internal Biometrics document that specifies the programming rules, including the precision for derived variables.

All individual subject data for subjects who were randomized or received study drug will be presented in individual subject data listings.

Continuous variables will be summarized using the following descriptive summary statistics: the number of subjects (n), mean, SD, standard error (SE), median, minimum value (min), and maximum value (max).

Categorical variables will be summarized using counts and percentages. Percentages will be presented to 1 decimal place unless otherwise specified.

Baseline value, unless otherwise specified, will be defined as the most recent non-missing measurement (scheduled or unscheduled) collected before administration of study drug.

Change (absolute change) from baseline will be calculated as:

Post baseline value - baseline value.

The treatment-emergent (TE) period will include the time from dosing with study drug to the Safety Follow-up Visit or 28 days after treatment / the last available visit (whichever is later) for subjects who do not have a Safety Follow-up Visit.

Unscheduled visits: Unscheduled visit measurements will be included in analysis as follows:

- In scheduled visit windows per specified visit windowing rules.
- In the derivation of baseline measurements
- In the derivation of maximum/minimum values and maximum/minimum changes from baseline values.
- In individual subject data listings as appropriate.

Visit window rules: The analysis visit windows for protocol-defined visits are provided in [Appendix B](#).

Repeated observations within the same visit window:

- For all efficacy parameters, if there are multiple measurements within a visit window, the record at the scheduled visit will be used. If there are no measurements at the scheduled visit, then 1) the record closest to the target day will be used; or 2) if there are multiple records with the same distance to the target day, the latest record will be used.
- For all safety parameters, if there are multiple measurements within a visit window, then 1) the record closest to the target day will be used; or 2) if there are multiple records with the same distance to the target day, the latest record will be used.

Incomplete or missing data: If the SCIM III self-care subscore, CUE-T score, or GRASSP Quantitative Prehension score at 6 months after treatment is missing after the visit windows rules have been applied, the score at the early termination visit will be carried forward for the analysis.

Outliers: No formal statistical analyses will be performed to detect and/or remedy the presence of statistical outliers.

Unless otherwise specified, the analyses will be done by treatment group (VX-210 3 mg, VX-210 9 mg, Placebo), as some subjects have already been dosed with 3 mg using protocol version 1.0.

VX-210 3 mg will only be used in the following analyses:

1. Background characteristics (disposition, demographics/baseline characteristics, prior/concomitant medications, etc.).
2. All safety analyses.

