8.1.4 Early Discontinuation

Early Termination Visit will be conducted when a subject withdraws or is withdrawn from the study (Section 9.4), or 1 or multiple study sites are closed (Section 13.2.7). Assessments at the Early Termination Visit are listed in Table 3-1. The Safety Follow-up Visit will be required in addition to the Early Termination Visit only for subjects who prematurely terminate from the study prior to Day 28 after treatment. Subjects who prematurely terminate from the study subsequent to Day 28 after treatment will only be required to complete the Early Termination Visit.

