12.3.1 General Considerations

All individual subject data for all individual subjects randomized or received study drug will be presented in data listings.

Continuous variables will be summarized using the following descriptive summary statistics: the number of subjects (n), mean, SD, standard error (SE), median, minimum value (min), and maximum value (max). The precision of the measurement for each continuous variable will be used to determine the number of decimal places to present in tables, figures, and derived listings. Unless otherwise specified, min and max values will be reported with the same precision as the units of measure; the mean, median, SD, and SE will be reported to 1 greater decimal place. Any values that require transformation to standard units (metric or International System [SI]) will be converted with the appropriate corresponding precision. Details will be provided in the SAP.

Categorical variables will be summarized using counts and percentages. Percentages will be presented to 1 decimal place.

Baseline value, unless otherwise specified, will be defined as the most recent non-missing measurement (scheduled or unscheduled) collected before administration of study drug.

Change (absolute change) from baseline will be calculated as postbaseline value - baseline value.

The treatment-emergent (TE) period will include the time from dosing with study drug to the Safety Follow-up Visit or 28 days after treatment for subjects who do not have a Safety Follow-up Visit.

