13.1.1.3 Documentation of Adverse Events

All AEs will be collected from the time ICF is signed until the following time points:

- For subjects who do not enroll: until time of screen failure (e.g., screen failure, withdrawal of consent)

- For enrolled subjects who have a Safety Follow-up Visit: through the Safety Follow-up Visit
- For enrolled subjects who do not have a Safety Follow-up Visit, the **latest** of:
 - 28 days after study drug treatment, or
 - The last study visit.

All subjects will be queried, using non-leading questions, about the occurrence of AEs at each study visit. When possible, a constellation of signs and/or symptoms will be identified as 1 overall event or diagnosis. All AEs for enrolled subjects will be recorded in the CRF and source document. AEs for subjects who are screened but not subsequently enrolled in the study will be recorded only in the subject's source documents. The following data will be documented for each AE:

- Description of the event
- Classification of “serious” or “nonserious”
- Date of first occurrence and date of resolution (if applicable)
- Severity
- Causal relationship to study drug(s)
- Action taken
- Outcome
- Concomitant medication or other treatment given

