13.1.2 Serious Adverse Events

13.1.2.1 Definition of a Serious Adverse Event

An SAE is any AE that meets any of the following outcomes:

- Fatal (death, regardless of cause, that occurs during participation in the study or occurs after participation in the study and is suspected of being a delayed toxicity due to administration of the study drug)
- Life-threatening, such that the subject was at immediate risk of death from the reaction as it occurred
- Inpatient hospitalization or prolongation of hospitalization
- Persistent or significant disability/incapacity (disability is defined as a substantial disruption of a person's ability to conduct normal life functions)
- Congenital anomaly or birth defect
- Important medical event that, based upon appropriate medical judgment, may jeopardize the subject or may require medical or surgical intervention to prevent 1 of the outcomes listed above (e.g., an allergic bronchospasm requiring intensive treatment in an emergency room or at home)

If a subject has a hospitalization or procedure (e.g., surgery) for an event or condition that occurred before the subject signed the ICF, and the hospitalization or procedure was planned before the subject signed the ICF, the hospitalization or procedure should not be considered to indicate an SAE, unless an AE caused the hospitalization or procedure to be rescheduled sooner or to be prolonged relative to what was planned. In addition, hospitalizations clearly not associated with an AE (e.g., social hospitalization for purposes of respite care) should not be considered to indicate an SAE.

Clarification will be made between the terms “serious” and “severe,” because they are not synonymous. The term “severe” is often used to describe the intensity (severity) of a specific event, as in mild, moderate, or severe myocardial infarction. The event itself, however, may be of relatively minor medical significance, such as a severe headache. This is not the same as “serious,” which is based on subject/event outcome or action described above, and is usually associated with events that pose a threat to a subject's life or functioning. Seriousness, not severity, serves as a guide for defining expedited regulatory reporting obligations.

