9.4.1 Adverse Events

For analysis purposes, AEs will be classified as pretreatment AEs, TEAEs, or post-treatment AEs, defined as follows:

- Pretreatment AE: Any AE that started prior to dosing with study drug.
- TEAE: Any AE that developed or worsened at or after dosing of study drug through the end of the TE period.
- Post-treatment AE: Any AE that developed or worsened beyond the TE period.

For AEs with missing or partial missing start dates, if there is no clear evidence that the AEs started before or after study treatment, then the AEs will be classified as pre-treatment AEs/TEAEs/post-treatment AEs. Imputation rules for missing or partial AE start date are defined in the [Appendix D](#).

AE summary tables will be presented for TEAEs only, overall and by treatment group, and will include the following:

- All TEAEs
- TEAEs by relationship
- TEAEs by maximal severity
- Serious TEAEs

- TEAEs leading to death

Summaries will be presented by MedDRA system organ class and preferred term using frequency counts and percentages (i.e., number and percentage of subjects with an event as well as total number of events). When summarizing the number and percentage of subjects with an event, subjects with multiple occurrences of the same AE or a continuing AE will be counted once, only the maximum severity level will be presented in the severity summaries, and the worst/highest relationship level in the relationship summaries.

An AE overview table will be provided.

A listing containing individual subject AE data for all deaths and other serious AEs will be provided separately. All AEs, including pre- and post-treatment AEs, will be presented in individual subject data listings.

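### A fatal AE that starts after both Day 28 and the last available visit is classed as post-treatment and appears in no AE summary table, including TEAEs leading to death

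*SAP*

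**What the plan says.** SAP 9.1 starts the TE period at dosing and ends it at the Safety Follow-up Visit where one takes place. The remaining case is worded as follows: "or 28 days after treatment / the last available visit (whichever is later) for subjects who do not have a Safety Follow-up Visit". Protocol 8.1.4 requires a Safety Follow-up Visit "only for subjects who prematurely terminate from the study prior to Day 28 after treatment", so nearly every subject followed past Day 28 falls under the later-of rule. SAP 9.1 does not say what counts as the last available visit.

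SAP 9.4.1 classifies AEs by when they develop or worsen. The class that is tabulated is defined as "TEAE: Any AE that developed or worsened at or after dosing of study drug through the end of the TE period". Later events fall into a separate class, defined as "Post-treatment AE: Any AE that developed or worsened beyond the TE period".

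On reporting it states: "AE summary tables will be presented for TEAEs only, overall and by treatment group, and will include the following". The tables that follow include all TEAEs, serious TEAEs and TEAEs leading to death. SAP 9.4 restricts every safety summary to TE-period data. Deaths, other serious AEs and post-treatment AEs go into listings.

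Protocol 13.1.1.3 introduces the AE collection period with "All AEs will be collected from the time ICF is signed until the following time points". For enrolled subjects without a Safety Follow-up Visit, the end point is again the later of 28 days after treatment and the last study visit. Protocol 13.1.2.1 counts as serious any "death, regardless of cause, that occurs during participation in the study".

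The TE period in protocol 12.3.1 is narrower: where no Safety Follow-up Visit takes place, it stops at 28 days, whatever later visits the subject attends. That difference from the SAP needs its own reconciliation. The point here remains under the SAP's wider definition.

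**The concern.** A subject who dies attends no further visit, so the TE period closes at the last visit before death, or at Day 28 if that is later. A fatal event that begins between visits falls outside the period. Had the subject survived to the next visit, the period would have extended past the onset date and the event would have been counted.

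Whether an event enters the by-arm tables therefore depends partly on what happened to the subject afterwards. A safety table should not have this property, least of all the table of events leading to death.

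Safety is part of the primary objective. With about 50 subjects per arm, one omitted death is 1/50, or about 2 percentage points, in that arm. SAP 10.1.3 applies the same general considerations to the interim safety tables, apart from visit windowing. If the study stops for futility, follow-up continues for safety only.

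**Working it through.** The plan gives no figure to reproduce, so the rule is applied directly.

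**Inputs**
- TE end = max(Day 28, last available visit), from SAP 9.1, for a subject without a Safety Follow-up Visit.
- An AE is tabulated if it starts by TE end, from SAP 9.4.1.
- Visit target days are 43, 91, 182 and 365, from SAP Appendix B.
- Assumptions: all visits before death were attended on target, there were no unscheduled visits, and the fatal event is new.

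**Single cases**

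| Onset day | Last visit | TE end | Class |
|---|---|---|---|
| 20 | 7 | 28 | TEAE, tabulated |
| 35 | 7 | 28 | post-treatment, listed only |
| 60 | 43 | 43 | post-treatment, listed only |
| 120 | 91 | 91 | post-treatment, listed only |
| 250 | 182 | 182 | post-treatment, listed only |

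A survivor with onset on Day 120 who attends the Day 182 visit has TE end of at least 182, so that event is tabulated.

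**Share of deaths excluded**

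For a death in an interval of length L with a lag from onset to death, onset falls after the start of the interval for a fraction max(0, 1 − lag/L) of death times. This is max(0, L − lag) days of that interval. The intervals are Days 28–43 (L = 15), 43–91 (48), 91–182 (91) and 182–365 (183), 337 days in total.

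| Lag (days) | Excluded days by interval | Sum | Share of 337 |
|---|---|---|---|
| 7 | 8 + 41 + 84 + 176 | 309 | 92% |
| 14 | 1 + 34 + 77 + 169 | 281 | 83% |
| 30 | 0 + 18 + 61 + 153 | 232 | 69% |
| 60 | 0 + 0 + 31 + 123 | 154 | 46% |
| 90 | 0 + 0 + 1 + 93 | 94 | 28% |

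The last column assumes deaths spread evenly over Days 28 to 365. If dosing is counted as Day 1, the floor becomes Day 29, the total is 336 days and the rounded shares do not change.

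The documents give no mortality rate, no distribution of time to death and no onset-to-death lag. The shares therefore describe how the rule behaves. They do not predict a number of deaths.

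**The case against.** Several arguments limit the point, and most of them stand in part.

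- **Day 28 floor.** A reader might infer that the TE period simply ends at the last visit attended. It does not. Fatal events through Day 28 are tabulated even when no visit follows onset.
- **Onset governs.** An AE that began inside the TE period and proved fatal later is still a TEAE leading to death. The lag calculation allows for this, and it is why the share falls as the lag grows.
- **Not fatality as such.** A reader might infer that events are removed because they were fatal. The rule turns on there being no later visit. It equally excludes a non-fatal event in a subject lost to follow-up. Death does, however, guarantee that no later visit occurs.
- **Undefined term.** SAP 9.1 uses unscheduled measurements in analysis, and the protocol allows clinically indicated laboratory tests and ECGs. If such a contact counts as a visit, a terminal illness with assessments could move TE end past onset. This would reduce the exclusions by an unknown amount, and it shows that the term needs a definition.
- **Deaths are not hidden.** SAP 9.4.1 lists all deaths and other serious AEs without restricting them to TEAEs. SAP 9.2.1 tabulates discontinuation reasons by arm, which may show death. IDMC safety reviews follow a separate SAP. The listing gives no by-arm comparison and the disposition table gives no event terms, so neither replaces a by-arm table of fatal AEs.

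**Conclusion.** The point holds in this form: for subjects without a Safety Follow-up Visit, a fatal AE that first develops or worsens after both Day 28 and the last available visit is post-treatment by definition. It is reported only in listings, while the same event in a subject who reaches the next visit is tabulated. This follows from the stated rules, on the natural reading that a death date is not itself a visit.

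Its size is uncertain. The excluded share runs from about 92% at a 7-day lag to 28% at 90 days, under evenly spread deaths, full attendance on target days and no unscheduled visits. A reader might take the upper figures to mean that most late deaths will be missing from the tables. The documents do not support that, because they supply neither the lag nor the timing of deaths, and the number of deaths among about 100 subjects could be small. What can be said is that the by-arm tables of serious and fatal TEAEs may be incomplete in a way that depends on outcome.

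**What to change.** In SAP 9.1, for AE classification in subjects without a Safety Follow-up Visit, end the TE period at the latest of Day 28, the last available visit, and the date of death or last contact. Define the last available visit to include unscheduled and Early Termination visits. Align the AE collection end point in protocol 13.1.1.3.

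Alternatively or in addition, add a by-arm table of all deaths and fatal AEs over the full follow-up. This repairs the mortality reporting without redefining the TE period, but it leaves non-fatal events in subjects lost to follow-up outside the tables.

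The cost is about one sentence in each document, or one extra table. SAP section 4 allows documented revisions before the final database lock and unblinding. AE onset date and fatal outcome are already recorded under protocol 13.1.1. A date of death or last contact is not among the AE fields listed there, so confirm that the CRF captures both. There is one small downside: if the new end point is applied to the whole TE period, the concomitant and post-treatment medication categories in SAP 9.2.3 and Appendix C shift slightly. Limiting the change to AEs, or using only the all-deaths table, avoids this.
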